**Treatment may not begin without confirmation from the Coordinating Center that the participant has been registered.**

### **5. TREATMENT PLAN**

#### **5.1 Treatment Regimen**

Ivosidenib will be administered orally every day for 28 consecutive days, defined as a treatment cycle. Appropriate dose modifications are described in Section 6. Reported adverse events and potential risks are described in Section 7. No investigational or commercial agents or therapies other than those described below may be administered with the intent to treat the participant's myeloid malignancy.

---

CONFIDENTIAL

This document is confidential. Do not disclose or use except as authorized.

The starting dose of ivosidenib (AG-120) will be 500mg orally daily. After 3 (or 6) participants are treated at 500mg daily, if this dose is tolerated, then an additional 10 participants will be treated at 500mg daily. If the 500mg daily dose is NOT tolerated in the initial cohort of participants, then the dose will be decreased to 250mg daily. If 250mg daily is tolerated, then an additional 10 participants will be treated at 250mg daily. The only doses studied will be 500mg daily and 250mg daily (the latter, if necessary).

The first cohort will consist of three participants. After the third participant is enrolled to the cohort, enrollment will be put on hold until all three participants have completed the first 28-day cycle. The period for dose-limiting toxicity (DLT) evaluation is the first 28-day cycle. Individual participants must receive at least 50% of the dosing to be DLT evaluable for that cohort. If this criteria is not met, the patient in that dose-escalation cohort may be replaced.

If one of three participants in a cohort experiences a DLT, then an additional 3 participants will be observed at that dose. The recommended phase 2 dose (RP2D) is defined as the highest dose level at which 0 or 1 of six participants experiences a dose-limiting toxicity.

Dose Escalation Schedule	
Dose Level	Dose of Ivosidenib
Level 1	250mg daily
Level 2 – Starting Dose	500mg daily

Once the RP2D is defined, an additional 10 participants will be enrolled at that dose.

If 250mg daily dosing is not tolerated, then the study will end without expansion.

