If the overall study is dose decreased to 250mg daily and there are still any participants receiving 500mg daily ivosidenib, those participants may continue to receive 500mg ivosidenib unless/until they develop a toxicity that requires a dose-reduction.

The participant will be required to maintain a medication diary of each dose of medication. He/she should record relevant information regarding study drug dosing in the diary (e.g. confirmation that each dose was taken, reasons for missed doses). The medication diary will be returned to clinic staff at the end of each cycle.

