#### **5.4 Definition of Dose-Limiting Toxicity (DLT)**

Dose-limiting toxicities will be evaluated during cycle 1 (first 28 days) of treatment. Toxicities will be graded and documented according to NCI CTCAE version 4.03.

Non-hematologic DLTs will be defined as any drug-related grade 3 or greater event.

The following exceptions will NOT be considered DLTs in this population:

- grade 3 nausea, vomiting, or diarrhea that lasts  $\leq$  72 hours and responds to medical intervention

Hematologic DLTs will be defined as any drug-related grade 4 neutropenia ( $ANC < 500/\mu L$ ) or thrombocytopenia (platelets  $< 25,000/\mu L$ ) that

- has not resolved to grade 1 or less within 14 days of holding ivosidenib, or
- resolves within 14 days, but then recurs after resuming study drug

Note that anemia is not included as a DLT.

Additionally, febrile neutropenia of any duration, and not due or attributable to the underlying disease or other extraneous causes such as infection, will be considered a DLT.

In addition, any  $\geq$  grade 2 non-hematologic toxicity that the participant finds intolerable or renders the participant unable to take 75% of the assigned doses (e.g. multiple dose interruptions) during the first cycle will be considered a DLT.

Management and dose modifications associated with the above events are outlined in Section 6.

Dosing will proceed within each cohort according to the following scheme.

Number of observed DLTs at a Given Dose Level	Decision Rule
0/3	3 additional evaluable patients will be treated at the dose level. If $\leq 1$ of the 6 treated patients experience a DLT, this is the RP2D. If $\geq 2$ of the 6 treated patients experience a DLT and current dose is dose level 2, de-escalate to dose level 1.
$\geq 2$	De-escalate to dose level 1 if current dose is dose level 2.

CONFIDENTIAL

This document is confidential. Do not disclose or use except as authorized.

1/3	Add 3 more patients at current dose level  a) If 0 of these 3 additional patients experience DLT, current dose is RP2D.  b) If $\geq 1$ of these 3 additional patients experience DLT, then de-escalate to dose level 1 if current dose is dose level 2.
$\leq 1/6$	Current dose is the RP2D

Subsequent (after cycle 1) cycles of ivosidenib will continue, with participants monitored for toxicity and adverse event reporting, but will not be used for DLT evaluation.

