## **5.6 Criteria for Taking a Participant Off Therapy**

Participants with persistent remission can continue receiving ivosidenib for 12 cycles.

Duration of therapy will depend on tolerance and evidence of disease progression. In the absence of treatment delays due to adverse event(s), treatment may continue for 12 cycles or until one of the following criteria applies:

- Disease progression
- Intercurrent illness that prevents further administration of treatment
- Unacceptable adverse event(s)
- Participant demonstrates an inability or unwillingness to comply with the oral medication regimen and/or documentation requirements
- Participant decides to withdraw from the protocol therapy
- General or specific changes in the participant's condition render the participant unacceptable for further treatment in the judgment of the treating investigator

Participants will be removed from protocol therapy when any of these criteria apply. Alternative care options will be discussed with the participant. The reason for removal from protocol therapy, and the date the participant was removed, must be documented in the case report form (CRF). The DF/HCC research team will update the relevant Off Treatment/Off Study information in the CTMS, OnCore. The Coordinating Center will update this information for external site participants.

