### **6.3 Non-Hematologic Toxicity (except QT prolongation)**

If at any time during ivosidenib dosing, a participant experiences a grade 3 or higher toxicity that is possibly, probably or definitely related to ivosidenib, drug must be held until the toxicity resolves to a grade 1 or lower. If it is during the first cycle (28 days) of dosing, the toxicity will be considered to be a DLT (see section 5.4). In participants with known Gilbert’s disease, grade 3 elevated bilirubin that is possibly, probably or definitely related to ivosidenib would not require study drug hold if the elevation is not due to liver GVHD or veno-occlusive disease. For these participants, study drug must be held for grade 4 elevated bilirubin and resolution/recurrence of toxicity to follow the instructions below in 6.3.1 and 6.3.2.

If and when ivosidenib is held in the midst of a cycle, the cycle day will not change, and once the drug is resumed it will be either on the day that that cycle has progressed to, or if the pause is beyond 28 days of a cycle, the resumption will be called the day 1 of the subsequent cycle.

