### 6.3.2 500 mg dosing

If the participant was at the 500mg daily dosing level when the toxicity occurred, and the toxicity resolves to  $\leq$  grade 1 *after* 14 days, but *before* 28 days (total) have elapsed, then dosing with ivosidenib can resume at the reduced dose of 250 mg daily. If the attributable toxicity recurs at  $\geq$  grade 3 (or grade 4 bilirubinemia in those with known Gilbert's disease – see above section 6.3) during the course of the study, then the participant will come off treatment and will remain on study only for survival and other outcomes.

If the participant was at the 500mg daily dosing level when the toxicity occurred, and it takes *less than* 14 days for the event to resolve to  $\leq$  grade 1, then dosing with ivosidenib can resume at 500mg daily. If the toxicity recurs at  $\geq$  grade 3 (or grade 4 bilirubinemia in those with known Gilbert's disease – see above section 6.3), then dosing will again be held. (This will be a DLT if it occurs during cycle 1). If the toxicity again resolves to  $\leq$  grade 1 within 28 days, then dosing with ivosidenib can resume at the reduced dose of 250mg daily. If the toxicity recurs yet again at  $\geq$  grade 3 (or grade 4 bilirubinemia in those with known Gilbert's disease – see above section 6.3), then the participant will come off treatment and will remain on study only for survival and other outcomes.

A participant who starts at 500mg daily dosing and is subsequently reduced to 250mg daily dosing due to toxicity can potentially increase back up to 500mg daily dosing if subsequent evaluation of the observed toxicity indicates no relation to study drug. Any such re-escalation must have the approval of the principal investigator, [name].

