### 12.2 Data Safety Monitoring

---

CONFIDENTIAL

This document is confidential. Do not disclose or use except as authorized.

The DF/HCC Data and Safety Monitoring Committee (DSMC) will review and monitor toxicity and accrual data from this study. The committee is composed of medical oncologists, research nurses, pharmacists and biostatisticians with direct experience in cancer clinical research. Information that raises any questions about participant safety will be addressed with the Overall PI and study team.

The DSMC will review each protocol up to four times a year or more often if required to review toxicity and accrual data. Information to be provided to the committee may include: up-to-date participant accrual; current dose level information; DLT information; all grade 2 or higher unexpected adverse events that have been reported; summary of all deaths occurring within 30 days of intervention for Phase I or II protocols; for gene therapy protocols, summary of all deaths while being treated and during active follow-up; any response information; audit results, and a summary provided by the study team. Other information (e.g. scans, laboratory values) will be provided upon request.

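### Section 6.3.2 still allows a restart at 500 mg after the trial has rejected that dose as not tolerated

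*Combined protocol and SAP*

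**What the plan says.** **Rejecting 500 mg.** Section 5.1: "If the 500mg daily dose is NOT tolerated in the initial cohort of participants, then the dose will be decreased to 250mg daily". The table in section 13 makes this two or more DLTs among three or six participants.

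**Those still on 500 mg at that point.** Section 5.1: "those participants may continue to receive 500mg ivosidenib unless/until they develop a toxicity that requires a dose-reduction".

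**What counts as a DLT.** Section 5.4: "Non-hematologic DLTs will be defined as any drug-related grade 3 or greater event", with an exception for grade 3 nausea, vomiting or diarrhea that is brief (up to 72 hours) and responds to treatment. Section 6.3 requires the drug to be held for a related grade 3 or higher event and adds: "If it is during the first cycle (28 days) of dosing, the toxicity will be considered to be a DLT".

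**The restart dose.** Section 6.3.2 covers a participant who was at 500 mg when the event occurred. If the event settles to grade 1 or below in under 14 days, "then dosing with ivosidenib can resume at 500mg daily". If settling takes more than 14 but less than 28 days, the restart is at 250 mg. After a restart at 500 mg, a grade 3 or higher recurrence means "then dosing will again be held", and any later restart is at 250 mg.

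**The concern.** Section 6.3.2 reads as written for a trial in which 500 mg is a live study dose. Section 5.1 brings it into a different situation, where 500 mg has been judged not tolerated in this population and new participants receive 250 mg. The only stop in the 5.1 sentence is a toxicity that requires a reduction, and a first event that settles in under 14 days requires none.

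So a participant can have a serious drug-related event at a rejected dose, be taken off drug for it, and be put back on that same dose. What is at stake is the safety of individual participants, not the dose decision or any estimate.

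**Working it through.** The plan gives no figure on this point. The check sets the rules in sequence and then works out when the gap is open.

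**1. Restart dose under 6.3.2 (related grade 3+ event at 500 mg)**

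| Course of the event | Restart dose |
|---|---|
| First event, settles in under 14 days | 500 mg |
| First event, settles after 14 but before 28 days | 250 mg |
| Recurrence after a 500 mg restart, settles within 28 days | 250 mg |

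Only the first row leads back to 500 mg. None of the rows depends on whether 500 mg is still a study dose.

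**2. Two cases after rejection**

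- *Case A: first event after rejection.* A participant without a DLT stays on 500 mg under 5.1. In a later cycle there is a related grade 3 transaminase rise (liver dysfunction is a listed risk in 7.1.2). Drug is held, the event settles in under 14 days, and row 1 applies. No reduction was required, so the 5.1 stop is not triggered and 500 mg can be restarted. This case is clear on the text.
- *Case B: on hold with a DLT at rejection.* Section 6.3.2 is keyed to the dose at the time of the event, so read literally row 1 still allows 500 mg. This case is weaker: the 5.1 permission speaks of people still receiving 500 mg, and 5.1 also says the dose will be decreased. That 6.3.2 survives rejection here is an inference from the absence of any text ending it.

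**3. How often the precondition arises**

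With p the true DLT rate at 500 mg, the 3+3 rule rejects 500 mg with probability

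P(reject) = A + (1−p)³·A + 3p(1−p)²·[1−(1−p)³], where A = 3p²(1−p) + p³.

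At p = 0.20: A = 0.104, and P = 0.104 + 0.512×0.104 + 0.384×0.488 = 0.104 + 0.053 + 0.187 = 0.345.

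| Assumed p | 0.10 | 0.20 | 0.30 | 0.40 |
|---|---|---|---|---|
| P(reject) | 0.114 | 0.345 | 0.580 | 0.767 |

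The rates p are assumptions; the documents give none.

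**4. How long the gap stays open for someone kept on 500 mg**

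Inputs: 12 cycles of 28 days (5.2.2); accrual of 1 to 2 per month (section 13). Assumed: evenly spaced starts (30.4 or 15.2 days apart) and a decision on the last participant's day 28.

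Cycles left = 12 − (decision day − own start day)/28.

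- Rejection after three: decision day 89 or 58. First participant: 12 − 89/28 = 8.8 or 12 − 58/28 = 9.9. Last participant: 12 − 28/28 = 11.
- Rejection after six, with no lag after the enrollment hold: decision day 178 or 117. First participant: 5.7 or 7.8. Last participant: 11.

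Enrollment precedes transplant, and dosing starts 30 to 90 days after it (5.2.1). A further 90-day lag for the second three lowers the 5.7 to 2.4, and a longer lag would lower it more.

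**5. What cannot be computed**

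The chance that a restart at a rejected dose actually occurs needs the rate of related grade 3+ non-hematologic events after rejection, the share settling in under 14 days, and how often investigators would choose 500 mg. The documents give none of these.

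**The case against.** **The 5.1 sentence looks deliberate.** It addresses exactly this event and makes each person's own toxicity the test; the cohort rule picks the dose for new participants. That stands. It matters most for a reading that a reader might infer: that anyone who had a DLT at 500 mg, including someone already back on 500 mg without recurrence, must be moved to 250 mg at rejection. The documents do not support that as a defect:

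- Such a participant carries direct evidence of re-tolerance. For a first participant with an event on day 8 and a restart on day 18, a decision on day 89 or 58 comes after about 71 or 40 further days at 500 mg. A grade 3+ recurrence would already have led to a hold, with any restart at 250 mg.
- The dose evidence points both ways. Section 2.3 reports tolerability up to 1200 mg with no maximum tolerated dose reached, and 500 mg is the dose in the other ivosidenib studies. Section 8.1.1 places 250 mg inside the 200 to 1200 mg range over which plasma 2-HG fell substantially, though not in post-transplant maintenance.
- Rejection alone is modest evidence about one person: it occurs 11% of the time even at a true DLT rate of 10%.

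Moving that participant down is a trade-off, and the plan's choice is defensible.

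**There are brakes.** The wording is permissive, and investigators can stop treatment where changes in condition "render the participant unacceptable for further treatment in the judgment of the treating investigator". The monitoring committee may receive "current dose level information; DLT information". Strong CYP3A4 inhibitors already force 250 mg (6.4). These reduce the risk, but none is tied to a restart at a rejected dose. The re-tolerance argument does not help either: in both cases in the working, the participant has not yet been rechallenged after the event.

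**Conclusion.** The point holds in a limited form. For related grade 3+ non-hematologic events other than QTcF and neurologic ones, 6.3.2 allows a restart at 500 mg after settling in under 14 days, and no visible text ends that permission once 500 mg has been rejected. The conclusion is firm for a first event after rejection in someone kept on 500 mg. It is literal but less certain for someone on hold with a DLT at rejection.

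The size is modest and unquantified. The gap needs rejection first (0.11 to 0.58 at assumed true DLT rates of 10% to 30%). It can then stay open for most of the planned treatment, on the accrual assumptions shown. A reader might want to attach a probability to the event itself; the documents give no basis for one.

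Nor should it be inferred that the dose finding is compromised: the RP2D rule, the sample size and the 16-patient toxicity estimate do not depend on this rule.

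Outside the point are QTcF (6.5 has its own reduction rules), neurologic toxicity (6.6 was not available for review) and hematologic toxicity (6.7).

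**What to change.** In 6.3.2, directly after "then dosing with ivosidenib can resume at 500mg daily" in the under-14-day rule, add:

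*unless the study has been decreased to 250mg under 5.1, in which case dosing resumes at 250mg daily and any grade 3 or higher recurrence is managed under 6.3.1.*

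The reference to 6.3.1 settles the next step: a recurrence after a restart at 250 mg takes the participant off treatment, as 6.3.2 already provides after a slow-settling first event.

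Leave the 5.1 continuation sentence as it stands for participants already back on 500 mg without recurrence. Optionally, require a documented review with the principal investigator at rejection for any of them who had a DLT. Leave 6.5, 6.6, 6.7.2 and the 6.3.2 clause on re-escalation after events found unrelated to drug unchanged.

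Cost: one clause, with no new patients, visits, data or analyses; 250 mg is the supplied tablet strength (8.1.2). The downside is that a few participants lose a same-dose rechallenge at 500 mg, the dose used in the other ivosidenib studies.

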## 5.2 Pre-Treatment Criteria

### 5.2.1 Cycle 1, Day 1

Treatment may begin at any time between day 30 and day 90 following stem cell transplantation. However, at time of treatment start, it must be ensured that:

- The patient has continued willingness and interest in participating in the study.
- Chimerism studies reveal that  $\geq 70\%$  of blood or bone marrow cells, or of the CD33 expressing fraction, are of donor origin,
- There is no acute graft versus host disease (GVHD), requiring an equivalent dose of  $\geq 0.5\text{mg/kg/day}$  of prednisone within one week of starting ivosidenib, or have escalation of systemic immunosuppression in terms of increase of corticosteroids or addition of new agent/modality within two weeks of starting ivosidenib.
- There is no evidence of relapsed/recurrent/residual disease.
- There is no systemic infection requiring IV antibiotic therapy within 7 days of starting ivosidenib

Prior to the start of ivosidenib administration, the participant must have adequate hematological function, defined as:

- ANC  $\geq 1000/\mu\text{L}$
- Platelets  $\geq 50,000/\mu\text{L}$

and adequate organ function defined as

- Direct bilirubin level  $< 2.0 \text{ mg/dL}$
- AST (SGOT), ALT (SGPT) and Alkaline phosphatase  $< 3x$  institutional upper limit of normal (ULN)
- Presence of congestive heart failure, defined by New York Heart Association (NYHA) criteria as class 3 or 4
- Calculated creatinine clearance  $\geq 40 \text{ mL/min}$  (Cockcroft-Gault formula)

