### 3. PARTICIPANT SELECTION

#### 3.1 Eligibility Criteria

Participants must meet the following criteria to be eligible for enrollment on this study.

- 3.1.1 Pathologically confirmed diagnosis of *IDH1(R132)*-mutant acute myeloid leukemia (AML), myelodysplastic syndrome (MDS) or chronic myelomonocytic leukemia (CMML). *IDH1* mutations could have been detected by any mutational technique at any prior point including at diagnosis or remission.
- 3.1.2 Age  $\geq 18$
- 3.1.3 Will undergo allogeneic hematopoietic stem cell transplantation (HSCT) for their malignancy. Conditioning may be either conventional myeloablative (MAC) or reduced intensity conditioning (RIC).
- 3.1.4 HSCT Donor will be one of the following:
  - 5/6 or 6/6 (HLA-A, B, DR) matched related donor
  - 7/8 or 8/8 (HLA-A, B, DR, C) matched unrelated donor. Matching in the unrelated setting must be at the allele level.
  - Haploidentical related donor, defined as  $\geq 3/6$  (HLA-A, B, DR) matched
  - $\geq 4/6$  (HLA-A, B, DR) umbilical cord blood (UCB). Matching in the UCB setting is at the antigen level. Recipients may receive either one or two UCB units. In the case of 2 UCB units, both units must have been at least 4/6 matched with the recipient.
- 3.1.5 ECOG performance status  $\leq 2$
- 3.1.6 Participants must have normal organ and marrow function as defined below:
  - Absolute neutrophil count  $\geq 1000/\mu\text{L}$  without growth factor support (e.g. GCSF) in the previous 7 days. This criterion does not apply to patients with myelodysplastic syndromes, myeloproliferative neoplasms in leukemic phase, or CMML, who will not necessarily be expected to achieve marrow recovery prior to HSCT.
  - Platelet count  $\geq 50,000/\mu\text{L}$  without transfusional support in the previous 7 days. This criterion does not apply to patients with myelodysplastic syndromes, myeloproliferative neoplasms in leukemic phase, or CMML, who will not necessarily be expected to achieve marrow recovery prior to HSCT.
  - AST (SGOT), ALT (SGPT) and Alkaline phosphatase  $< 3x$  institutional upper limit of normal (ULN)
  - Direct bilirubin  $< 2.0 \text{ mg/dL}$
  - Calculated creatinine clearance  $\geq 40 \text{ mL/min}$  (Cockcroft-Gault formula)

---

CONFIDENTIAL

This document is confidential. Do not disclose or use except as authorized.

- 3.1.7 LVEF must be equal to or greater than 40%, as measured by MUGA scan or echocardiogram

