## **3.2 Exclusion Criteria**

Participants meeting any of the following criteria are not eligible for study enrollment:

- 3.2.1 Prior allogeneic hematopoietic stem cell transplants.
- 3.2.2 For patients with acute myeloid leukemia, morphologically relapsed or refractory disease, as assessed by bone marrow aspirate and biopsy performed within 42 days prior to study entry, is exclusionary. For patients with myelodysplastic syndromes or chronic myelomonocytic leukemia, the presence of less than 5% myeloblasts is allowed on a bone marrow biopsy within 42 days prior to study entry.
- 3.2.3 History of other malignancy(ies) unless
  - the participant has been disease-free for at least 5 years and is deemed by the investigator to be at low risk of recurrence of that malignancy, or
  - the only prior malignancy was cervical cancer in situ and/or basal cell or squamous cell carcinoma of the skin
- 3.2.4 Known diagnosis of active hepatitis B or hepatitis C
- 3.2.5 Current or history of congestive heart failure New York Heart Association (NYHA) class 3 or 4, or any history of documented diastolic or systolic dysfunction (LVEF < 40%, as measured by MUGA scan or echocardiogram)
- 3.2.6 Current or history of ventricular or life-threatening arrhythmias or diagnosis of long-QT syndrome
- 3.2.7 QTc interval (i.e., Fridericia's correction [QTcF])  $\geq$  450 ms or other factors that increase the risk of QT prolongation or arrhythmic events (e.g., heart failure, hypokalemia, family history of long QT interval syndrome) at screening
- 3.2.8 Systemic uncontrolled infection

---

CONFIDENTIAL

This document is confidential. Do not disclose or use except as authorized.

- 3.2.9 Uncontrolled intercurrent illness that would limit compliance with study requirements.
- 3.2.10 HIV-positive participants on combination antiretroviral therapy are ineligible because of the potential for pharmacokinetic interactions with study drug. In addition, these participants are at increased risk of lethal infections when treated with marrow-suppressive therapy.

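### Section 5.2.1 makes the presence, not the absence, of NYHA class 3–4 heart failure a condition for the first dose, contrary in direction to exclusion 3.2.5.

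*Combined protocol and SAP*

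**What the plan says.** Section 5.2.1 (Cycle 1, Day 1) gives the conditions for starting ivosidenib. The requirement is mandatory: "Prior to the start of ivosidenib administration, the participant must have adequate hematological function, defined as" limits for neutrophils and platelets, "and adequate organ function defined as" four further items. Three of the four describe an acceptable state (direct bilirubin, liver enzymes, creatinine clearance). The other reads "Presence of congestive heart failure, defined by New York Heart Association (NYHA) criteria as class 3 or 4".

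At enrolment the protocol takes the opposite position. Exclusion 3.2.5 rules out "Current or history of congestive heart failure New York Heart Association (NYHA) class 3 or 4". Exclusion 3.2.7 rules out "factors that increase the risk of QT prolongation or arrhythmic events (e.g., heart failure, hypokalemia, family history of long QT interval syndrome) at screening". Inclusion 3.1.7 adds that "LVEF must be equal to or greater than 40%, as measured by MUGA scan or echocardiogram".

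Enrolment and first dose are separate steps. Under 3.1.3 a participant enrols as someone who "Will undergo allogeneic hematopoietic stem cell transplantation (HSCT) for their malignancy", and the study calendar (Section 10) labels the screening column as pre-HSCT. Section 5.2.1 then states: "Treatment may begin at any time between day 30 and day 90 following stem cell transplantation".

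**The concern.** Read literally, 5.2.1 makes severe heart failure a requirement for dosing. If the correct rule were stated elsewhere for the same time point, this would be a cosmetic error, but it is not stated. Every correctly worded cardiac criterion belongs to enrolment, and conditioning and transplant fall between enrolment and first dose. By repeating the haematological, hepatic and renal limits at Day 1 and adding a heart-failure item, the protocol shows that it meant to check cardiac status again. That second check is the one that is reversed.

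The item has safety content. The protocol names heart failure as a factor that raises QT and arrhythmia risk (3.2.7), lists QT prolongation as an expected reaction to ivosidenib (7.1.1), and warns that azoles, fluoroquinolones and 5-HT3 antagonists may add to the risk (5.5.1, 6.5). The study is multicentre, and its eligibility criteria are monitored against the text. A checklist copied from 5.2.1 would carry the error, and a site that follows the evident intent would depart from the written rule.

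**Working it through.** No formula applies, because the point concerns wording. The check compares 5.2.1 with the enrolment criteria item by item, then looks for any other text that states the correct rule at treatment start.

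**Step 1. Direction of each item.**

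| Item in 5.2.1 | Enrolment counterpart | Direction |
|---|---|---|
| ANC ≥ 1000/µL | 3.1.6, same cut-off | Agrees |
| Platelets ≥ 50,000/µL | 3.1.6, same cut-off | Agrees |
| Direct bilirubin < 2.0 mg/dL | 3.1.6, same cut-off | Agrees |
| AST, ALT, alkaline phosphatase < 3x ULN | 3.1.6, same cut-off | Agrees |
| Creatinine clearance ≥ 40 mL/min | 3.1.6, same cut-off | Agrees |
| NYHA class 3–4 heart failure: present | 3.2.5: excluded | Reversed |

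Five of six agree and one is reversed. For ANC and platelets only the numerical cut-offs match: 3.1.6 also has a 7-day condition on growth factor or transfusion support and an exemption for MDS and CMML, neither of which is in 5.2.1. That does not affect the direction.

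**Step 2. What the literal text implies.** A participant who passes 3.2.5 has no current or past class 3–4 heart failure at enrolment. To meet 5.2.1 as written, the same participant must have it at Day 1. Taken together, the two rules admit only someone who develops severe heart failure between enrolment and first dose. This cannot be intended, which confirms a drafting error.

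**Step 3. Gap between the correct criteria and dosing.** The enrolment criteria are applied before transplant and dosing starts on day 30 to 90 after it. The gap is therefore 30 to 90 days plus the interval from screening to transplant. The protocol does not give that interval, so no total can be stated.

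**Step 4. Is the correct rule stated elsewhere for treatment start?**
- The general conditions at the head of 5.2.1 cover willingness, chimerism, GVHD, disease status and infection. None is cardiac.
- Section 5.2.1 has no LVEF or QTc criterion.
- The study calendar marks echocardiogram or MUGA at screening only.
- Calendar footnote 3 refers back to the laboratory criteria in 5.2.1 and does not restate the heart-failure item.
- The calendar does schedule medical history, physical examination and vital signs at pre-treatment, and an ECG on Cycle 1 Day 1. These could detect heart failure, but no criterion is attached to them that would stop dosing on that ground.

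The heart-failure item in 5.2.1 is therefore the only explicit one at treatment start.

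**Step 5. Extraction fault?** The sentence is complete, with no redaction mark, gap or broken table around it. Nothing suggests that a negation was lost in reading the PDF.

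**The case against.** The strongest reply is that the error has little practical effect. The bullet sits under a heading about adequate organ function, the literal reading would leave almost nobody to treat, and any investigator would take it as an exclusion. The intended check would then probably work, and it is hard to describe a realistic route by which a patient with class 3–4 heart failure is dosed because of this wording. Other safeguards also exist: issues that would delay treatment are to be discussed with the overall principal investigator (4.1), intercurrent illness or investigator judgement can end therapy (5.6), and ECG and electrolytes are monitored at least weekly in cycle 1 where QT-prolonging or strong CYP3A4-inhibiting drugs are used (5.5, 6.5). Section 5.2.1 does not cancel 3.2.5, which still governs enrolment. And nobody chose this rule, so it is a wording fault and not a flaw in the design.

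Most of this stands. The intent is obvious, 3.2.5 remains in force at enrolment, and the safeguards lower the residual risk. None of them, however, is a heart-failure criterion for the first dose, so the narrow point is untouched: the one explicit rule at that time says the opposite of what is meant. An obvious intent makes the correction easy; it does not make a reversed mandatory criterion acceptable.

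**Conclusion.** The concern holds. One of the six blood-count and organ-function items required before first dose is worded in reverse, and no other text states the correct rule for that time point. The weight is moderate: the line should be corrected because it is an operative safety criterion, but sites would probably read it as intended. The 3+3 decision rules, the sample size of 6 to 22 evaluable patients and the precision statement in Section 13 are unaffected.

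The conclusion rests on two readings of the text: that enrolment precedes transplant (3.1.3 and the calendar's pre-HSCT screening column), and that the 5.2.1 list is mandatory, as its lead-in says.

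**What to change.** In 5.2.1, replace *Presence* with *Absence* at the start of the heart-failure item, leaving the rest of the line as it is. This brings it into line with the direction of 3.2.5. Any site checklist or form derived from 5.2.1 should be checked for the same wording.

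The cost is a one-word protocol amendment. It adds no procedure and excludes nobody the sponsor meant to treat. It does not reproduce all of 3.2.5 at Day 1, since past heart failure and LVEF would still be assessed only at screening; correcting the reversed line does not depend on changing that.
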